### **3.6.2 Lost to Follow-Up**

All reasonable efforts must be made to locate subjects to determine and report their ongoing status. This includes follow-up with persons authorized by the subject as noted above. Lost to follow-up is defined by the inability to reach the subject after a minimum of three documented phone calls, faxes, or emails as well as lack of response by subject to one registered mail letter. All attempts should be documented in the subject's medical records. If it is determined that the subject has died, the site will use permissible local methods to obtain the date and cause of death.

If investigator's use of third-party representative to assist in the follow-up portion of the study has been included in the subject's informed consent, then the investigator may use a Sponsor-retained third-party representative to assist site staff with obtaining subject's contact information or other public vital status data necessary to complete the follow-up portion of the study. The site staff and representative will consult publicly available sources, such as public health registries and databases, in order to obtain updated contact information. If after all attempts, the subject remains lost to follow-up, then the last known alive date as determined by the investigator should be reported and documented in the subject's medical records.

## **4 STUDY DRUG**

Study drug includes both Investigational [Medicinal] Product (IP/IMP) and Non-investigational [Medicinal] Product (Non-IP/Non-IMP) and can consist of the following:

- Study required premedication (if applicable)

**Table 4-1: Study Drugs for CA209384**

Product Description / Class and Dosage Form	Potency	IP/Non-IMP	Blinded or Open Label	Packaging/ Appearance	Storage Conditions (per label)
Nivolumab Solution for Injection	100 mg (10 mg/mL)	10 mL per vial/	5 vials per carton/ Open-label	Clear to opalescent colorless to pale yellow liquid. May contain particles	2 to 8°C. Protect from light and freezing

#### **4.1 Investigational Product**

An investigational product, also known as investigational medicinal product in some regions, is defined a pharmaceutical form of an active substance or placebo being tested or used as a reference in a clinical study, including products already with a marketing authorization but used or assembled (formulated or packaged) differently than the authorized form, or used for an unauthorized indication, or when used to gain further information about the authorized form.

The investigational product should be stored in a secure area according to local regulations. It is the responsibility of the investigator to ensure that investigational product is only dispensed to study subjects. The investigational product must be dispensed only from official study sites by authorized personnel according to local regulations.

The investigational product in this study is nivolumab, which will be provided at randomization.

#### **4.2 Non-investigational Product**

Other medications used as support or escape medication for preventative, diagnostic, or therapeutic reasons, as components of the standard of care for a given diagnosis, may be considered as non-investigational products.

Not applicable.

#### **4.3 Storage and Dispensing**

The product storage manager should ensure that the study drug is stored in accordance with the environmental conditions (temperature, light, and humidity) as determined by BMS. If concerns regarding the quality or appearance of the study drug arise, the study drug should not be dispensed and contact BMS immediately.

Study drug not supplied by BMS will be stored in accordance with the package insert.

Investigational product documentation (whether supplied by BMS or not) must be maintained that includes all processes required to ensure drug is accurately administered. This includes documentation of drug storage, administration and, as applicable, storage temperatures, reconstitution, and use of required processes (eg, required diluents, administration sets).

#### **4.4 Method of Assigning Subject Identification**

CA209384 is a randomized study. After the subject's eligibility is established and informed consent has been obtained, the subject will be enrolled, and a number will be assigned through an interactive web-based response system (IWRS). Specific instructions for enrollment and randomization procedures using IWRS will be provided to the investigational site in a separate document/manual. Subjects meeting all eligibility criteria and randomized into the study will be assigned to 1 of the 2 treatment arms and stratified by the following factors: histology and response at randomization (CR or PR vs SD).

Required information for registration includes, but is not limited to, the following:

- Response at randomization (CR or PR vs SD)

- Subject received and tolerated nivolumab either 3 mg/kg or 240 mg every 2 weeks for up to 12 months (52 weeks)
- ECOG status 0-2
- Planned date of randomization

Additional information required for registration in the study will be available in a separate document.

IWRS code will be provided to the analytical laboratories and to the PK and immunogenicity scientists to facilitate PK and immunogenicity sample analysis.

#### **4.5 Selection and Timing of Dose for Each Subject**

Subjects will be enrolled after receiving up to 12 months (52 weeks) of nivolumab therapy at 240 mg or 3 mg/kg Q2W and after achieving a CR, PR, or SD, confirmed on 2 consecutive tumor assessments.

Subjects in Arm 1 will receive 240 mg of nivolumab intravenously as a 30-minute ( $\pm$  5 minutes) IV infusion on Day 1 of each treatment cycle every 2 weeks, until progression, unacceptable toxicity, withdrawal of consent, or the subject reaches a maximum of 2 years from the first on-study dose, or the study ends, whichever occurs first. In this arm, each 14-day dosing period will constitute a cycle.

Subjects in Arm 2 will receive 480 mg nivolumab as a 30-minute ( $\pm$  5 minutes) IV infusion on Day 1 of each treatment cycle every 4 weeks until progression, unacceptable toxicity, withdrawal of consent, or the subject reaches a maximum of 2 years from the first on-study dose, whichever occurs first. In this arm, each 28-day dosing period will constitute a cycle.

Subjects in Arm 1 may be dosed no less than 12 days from the previous dose; subjects in Arm 2 may be dosed no less than 26 days from the previous dose.

No dose escalations or reductions of nivolumab are allowed. There are no premedications recommended for nivolumab until infusion reactions have been observed in the subject. Subjects should be carefully monitored for infusion reactions during nivolumab administration. If an acute infusion reaction is noted, subjects should be managed according to [Section 4.5.5](#).

Dose delay criteria, criteria to resume treatment, and dose discontinuation criteria can be found in [Section 4.5.1](#), [Section 4.5.2](#), and [Section 4.5.3](#), respectively.

##### **4.5.1 Dose Delay Criteria**

Nivolumab administration should be delayed for the following:

- Grade 2 non-skin drug related AEs, with the exception of fatigue
- Grade 2 drug-related creatinine, AST, ALT and/or Total Bilirubin abnormalities
- Any Grade 3 skin, drug-related AE
- Any Grade 3 drug-related laboratory abnormality, with the following exceptions:
  - Grade 3 lymphopenia or asymptomatic amylase or lipase does not require dose delay
  - Grade  $\geq$  3 AST, ALT, Total Bilirubin will require dose discontinuation

- Any AE, laboratory abnormality, or intercurrent illness which, in the judgment of the investigator, warrants delaying the dose of study medication.

Subjects who require delay of nivolumab should be re-evaluated weekly or more frequently if clinically indicated and resume nivolumab dosing when re-treatment criteria are met.

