#### **4.5.2 Criteria to Resume Treatment**

Subjects may resume treatment with nivolumab when the drug-related AE(s) resolve(s) to Grade  $\leq$  1 or baseline, with the following exceptions:

- Subjects may resume treatment in the presence of Grade 2 fatigue
- Subjects who have not experienced a Grade 3 drug-related skin AE may resume treatment in the presence of Grade 2 skin toxicity
- For subjects with Grade 2 AST, ALT and/or Total Bilirubin Abnormalities, dosing may resume when laboratory values return to baseline and management with corticosteroids, if needed, is complete.
- Drug-related pulmonary toxicity, diarrhea, or colitis must have resolved to baseline before treatment is resumed. Subjects with persistent Grade 1 pneumonitis after completion of a steroid taper over at least 1 month may be eligible for retreatment if discussed with and approved by the Medical Monitor or designee.

Subjects with drug-related endocrinopathies adequately controlled with only physiologic hormone replacement may resume treatment after consultation with the BMS Medical Monitor (or designee). Adrenal insufficiency requires discontinuation regardless of control with hormone replacement.

Dose interruption of nivolumab which results in treatment interruption of  $>$  6 weeks require treatment discontinuation, with exceptions as noted in Section 4.5.3. There will be no dose reductions for nivolumab.

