#### **4.5.3 Dose Discontinuation Criteria**

Nivolumab treatment should be permanently discontinued for the following:

- Any Grade 2 drug-related uveitis, eye pain, or blurred vision that does not respond to topical therapy and does not improve to Grade 1 severity within the re-treatment period OR requires systemic treatment
- Any Grade 3 non-skin, drug-related AE lasting  $>$  7 days, with the following exceptions for laboratory abnormalities, drug-related uveitis, pneumonitis, bronchospasm, hypersensitivity reactions, infusion reactions, and endocrinopathies:
  - Grade 3 drug-related uveitis, pneumonitis, bronchospasm, neurologic toxicity, myocarditis, hypersensitivity reaction, or infusion reaction of any duration requires discontinuation
  - Grade 3 drug-related endocrinopathies adequately controlled with only physiologic hormone replacement do not require discontinuation. Adrenal insufficiency requires discontinuation regardless of control with hormone replacement.
  - Grade 3 drug-related laboratory abnormalities do not require treatment discontinuation except:

- ◆ Grade 3 drug-related thrombocytopenia > 7 days or associated with bleeding requires discontinuation
- ◆ Grade  $\geq$  3 drug-related AST, ALT or Total Bilirubin requires discontinuation\*
- ◆ Concurrent AST or ALT > 3 x ULN and total bilirubin > 2 x ULN

\*In most cases of Grade 3 AST or ALT elevation, study treatment will be permanently discontinued. If the investigator determines a possible favorable benefit/risk ratio that warrants continuation of study treatment, a discussion between the investigator and the BMS Medical Monitor/designee must occur.

- Any Grade 4 drug-related AE or laboratory abnormality, except for the following events which do not require discontinuation:
  - Grade 4 neutropenia  $\leq$  7 days
  - Grade 4 lymphopenia or leukopenia or asymptomatic amylase or lipase
  - Isolated Grade 4 electrolyte imbalances/abnormalities that are not associated with clinical sequelae and are corrected with supplementation/appropriate management within 72 hours of their onset
  - Grade 4 drug-related endocrinopathy AE, such as adrenal insufficiency, hyper- or hypothyroidism, or glucose intolerance, which resolve or are adequately controlled with physiologic hormone replacement (corticosteroids, thyroid hormones) or glucose-controlling agents, respectively, may not require discontinuation after discussion with and approval from the Medical Monitor.

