## **APPENDIX 2      MANAGEMENT ALGORITHMS**

These general guidelines constitute guidance to the Investigator and may be supplemented by discussions with the Medical Monitor representing the Sponsor. The guidance applies to all immuno-oncology agents and regimens.

A general principle is that differential diagnoses should be diligently evaluated according to standard medical practice. Non-inflammatory etiologies should be considered and appropriately treated.

[figure not shown]
Corticosteroids are a primary therapy for immuno-oncology drug-related adverse events. The oral equivalent of the recommended IV doses may be considered for ambulatory patients with low-grade toxicity. The lower bioavailability of oral corticosteroids should be taken into account when switching to the equivalent dose of oral corticosteroids.

Consultation with a medical or surgical specialist, especially prior to an invasive diagnostic or therapeutic procedure, is recommended.

The frequency and severity of the related adverse events covered by these algorithms will depend on the immuno-oncology agent or regimen being used.

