## Skin Adverse Event Management Algorithm

Rule out non-inflammatory causes. If non-inflammatory cause, treat accordingly and continue I-O therapy.

Patients on IV steroids may be switched to an equivalent dose of oral corticosteroids (e.g. prednisone) at start of tapering or earlier, once sustained clinical improvement is observed. Lower bioavailability of oral corticosteroids should be taken into account when switching to the equivalent dose of oral corticosteroids.

[figure not shown]
\*Refer to NCI CTCAE v4 for term-specific grading criteria.

^If SJS/TEN is suspected, withhold I-O therapy and refer patient for specialized care for assessment and treatment. If SJS or TEN is diagnosed, permanently discontinue I-O therapy.

Updated 05-Jul-2016

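### A diagnosed, drug-related SJS or TEN case graded 3 is a delay with possible resumption under Protocol Sections 4.5.1 to 4.5.3 but a permanent stop under the Appendix 2 skin footnote, and no text says which prevails

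*Protocol*

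**What the plan says.** Section 4.5.1 places "Any Grade 3 skin, drug-related AE" among the reasons to delay a dose and tells the site to re-evaluate the subject and "resume nivolumab dosing when re-treatment criteria are met".

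Section 4.5.2 sets those criteria. The general rule begins "Subjects may resume treatment with nivolumab when the drug-related AE(s) resolve(s) to Grade" and puts the threshold at Grade 1 or less, or baseline. Its one skin-specific line is "Subjects who have not experienced a Grade 3 drug-related skin AE may resume treatment in the presence of Grade 2 skin toxicity".

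Section 4.5.3 requires permanent discontinuation for "Any Grade 3 non-skin, drug-related AE lasting" more than 7 days. Its list of Grade 3 events that stop treatment at any duration names neither SJS nor TEN. Its Grade 4 rule covers "Any Grade 4 drug-related AE or laboratory abnormality, except for the following events which do not require discontinuation", and no skin event is among those exceptions.

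Appendix 2, in the footnote to the skin algorithm, says to withhold treatment when SJS/TEN is suspected, and then: "If SJS or TEN is diagnosed, permanently discontinue I-O therapy".

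On the standing of these texts, Section 3.5 makes the Section 4.5.3 criteria mandatory reasons to stop. Section 4.5.4 sends the site to the algorithms, skin included. Appendix 2 opens with "These general guidelines constitute guidance to the Investigator".

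**The concern.** For one kind of event, the sections that control dosing and the appendix give different instructions. Section 3.5 sends the site to Section 4.5.3 for mandatory stopping, and that section does not mention SJS or TEN. The text that does mention them describes itself as guidance.

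The main stake is subject safety: whether a subject may be dosed again after a diagnosed severe skin reaction could depend on which page the site relies on. Enrollment has stopped, but treatment runs for up to 2 years from the first randomized dose, so the rules still apply to anyone on treatment.

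The secondary stake is classification. AEs leading to discontinuation and AEs leading to dose delay are reported by arm (Protocol Section 8.4.3; SAP Sections 7.6.4 and 7.6.7.1), and the same event could be counted under either heading. The co-primary PFS rates are not directly touched: under Protocol Section 8.3.1, stopping for toxicity is neither a PFS event nor a reason for censoring.

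**Working it through.** The core of this is a comparison of texts. Taking a drug-related case by grade:

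| Case | Sections 4.5.1 to 4.5.3 | Appendix 2 skin footnote | Result |
|---|---|---|---|
| Suspected, Grade 1-2 | No skin-specific delay; delay available on investigator judgment (4.5.1) | Withhold and refer | Gap in wording, no contradiction |
| Diagnosed, Grade 3 | Delay (4.5.1); may resume at Grade 1 or less or baseline (4.5.2); outside the Grade 3 stopping rule (4.5.3) | Permanently discontinue | Conflict |
| Diagnosed, Grade 4 | Permanently discontinue (4.5.3) | Permanently discontinue | Agreement |

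**The Grade 3 row, step by step.**
1. Section 4.5.1 makes the event a delay.
2. The skin line in Section 4.5.2 lets subjects *without* a Grade 3 skin event resume at Grade 2. A subject who has had one loses that option and falls back on the general threshold. The line does not bar resumption.
3. Section 4.5.3 limits its Grade 3 rule to non-skin events, so it does not apply.
4. The footnote wording names no grade, so on its face it does apply.

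**Does any other text settle it?**
- Section 4.5.4 links to the algorithms but does not say which text governs.
- The judgment clauses in Sections 3.5, 4.5.1 and 4.5.3 allow a delay or a stop, but each depends on the investigator's opinion.
- The limit of 6 weeks from the previous dose in Section 4.5.3 would stop some cases, but it exempts prolonged steroid tapers for drug-related events, and approved delays for non-drug-related reasons.
- SAP Section 7.4.2.1 repeats the 6-week limit and adds nothing on SJS/TEN.

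**Size.** The documents give no SJS/TEN rate. The nearest figures count Grade 3-4 skin select AEs of every kind on nivolumab, scaled here to the approximately 350 subjects expected:
- CA209017, drug-related (Protocol Table 1.4.2-1): 0/131, so a point estimate of 0 subjects. The exact two-sided 95% upper limit is 1 − 0.025^(1/131) = 2.8%, and 0.028 × 350 ≈ 10.
- CA209017, all-cause (same table): 1/131 = 0.76%, and 0.0076 × 350 = 2.7 subjects.
- CA209057 (Protocol Section 1.4.2): Grade 3-4 select AEs at 3% or less in the categories listed, skin included; 0.03 × 350 = 10.5 as a ceiling.

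The first figure matches the rule, which concerns drug-related events. SJS/TEN would be a subset of any of these counts, and Grade 3 cases a subset of that.

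**The case against.** The strongest reply is that the texts can be followed together. Section 4.5.2 says subjects *may* resume, so a site that stops for good on diagnosis breaches nothing in Sections 4.5.1 to 4.5.3. The footnote can be read as a diagnosis-specific instruction on top of general grade-based rules, and Section 4.5.4 puts the algorithms in front of the same investigator. This stands in part: a cautious site can comply with both. But a site that resumes dosing also complies with Sections 4.5.1 to 4.5.3, and no text tells it that the footnote overrides them. Where Section 4.5.2 wants a stop despite control of the event, as for adrenal insufficiency, it says so.

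Three further objections limit the point:
- The algorithm figure is not shown. The footnote mark attaches to something in it, possibly a particular grade. If the figure confined the footnote to Grade 4, the conflict would disappear.
- The documents do not grade SJS or TEN; the algorithm refers to CTCAE v4 for grading. The conflict needs a Grade 3 case to be possible.
- The rates come from subjects starting nivolumab. Subjects here had already tolerated it, and in CA209017 most subjects with a treatment-related select AE had it within 3 months of the first dose. The scaled figures may therefore be too high.

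A reader might go further and infer that suspected SJS/TEN with low-grade skin findings is a second contradiction. It is not: Section 4.5.1 allows a delay for any AE that the investigator judges to warrant one. Nor is investigator judgment the only link between the two texts, because Section 4.5.4 points directly to the skin algorithm.

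**Conclusion.** There is a real inconsistency, confined to a diagnosed, drug-related SJS or TEN case graded 3. The judgment clauses and the 6-week limit make re-dosing less likely but do not supply one clear rule.

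Two stronger readings are not supported. A reader might infer that every diagnosed SJS or TEN case falls under conflicting rules; at Grade 4, Section 4.5.3 and the footnote agree. A reader might also take the all-cause 1/131 to mean that about 3 of 350 subjects would be affected; the rule covers drug-related events, for which the same table shows 0/131, and SJS/TEN is only a subset of skin events.

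Few if any subjects would be affected, and arm-level safety summaries are unlikely to move materially. The point rests on the consequence for a single subject, not on frequency. It assumes that SJS or TEN can be graded 3 and that the footnote applies as its wording reads, without a grade limit set by the missing figure. No view is taken on which rule is right.

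**What to change.** Reconcile Sections 4.5.1, 4.5.2 and 4.5.3 with the Appendix 2 skin footnote so that one rule governs diagnosed SJS/TEN. State it or cross-reference it in Section 4.5.3, where Section 3.5 sends the site, and have Section 4.5.2 say whether its resumption criteria apply to such cases. A sentence in Section 4.5.4 on which text governs when the two differ would close the precedence gap. The sponsor's medical team decides which rule stands.

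The cost is a change of wording in the protocol, with no extra procedures, data or subjects.

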#### **4.5.2 Criteria to Resume Treatment**

Subjects may resume treatment with nivolumab when the drug-related AE(s) resolve(s) to Grade  $\leq$  1 or baseline, with the following exceptions:

- Subjects may resume treatment in the presence of Grade 2 fatigue
- Subjects who have not experienced a Grade 3 drug-related skin AE may resume treatment in the presence of Grade 2 skin toxicity
- For subjects with Grade 2 AST, ALT and/or Total Bilirubin Abnormalities, dosing may resume when laboratory values return to baseline and management with corticosteroids, if needed, is complete.
- Drug-related pulmonary toxicity, diarrhea, or colitis must have resolved to baseline before treatment is resumed. Subjects with persistent Grade 1 pneumonitis after completion of a steroid taper over at least 1 month may be eligible for retreatment if discussed with and approved by the Medical Monitor or designee.

Subjects with drug-related endocrinopathies adequately controlled with only physiologic hormone replacement may resume treatment after consultation with the BMS Medical Monitor (or designee). Adrenal insufficiency requires discontinuation regardless of control with hormone replacement.

Dose interruption of nivolumab which results in treatment interruption of  $>$  6 weeks require treatment discontinuation, with exceptions as noted in Section 4.5.3. There will be no dose reductions for nivolumab.

#### **4.5.3 Dose Discontinuation Criteria**

Nivolumab treatment should be permanently discontinued for the following:

- Any Grade 2 drug-related uveitis, eye pain, or blurred vision that does not respond to topical therapy and does not improve to Grade 1 severity within the re-treatment period OR requires systemic treatment
- Any Grade 3 non-skin, drug-related AE lasting  $>$  7 days, with the following exceptions for laboratory abnormalities, drug-related uveitis, pneumonitis, bronchospasm, hypersensitivity reactions, infusion reactions, and endocrinopathies:
  - Grade 3 drug-related uveitis, pneumonitis, bronchospasm, neurologic toxicity, myocarditis, hypersensitivity reaction, or infusion reaction of any duration requires discontinuation
  - Grade 3 drug-related endocrinopathies adequately controlled with only physiologic hormone replacement do not require discontinuation. Adrenal insufficiency requires discontinuation regardless of control with hormone replacement.
  - Grade 3 drug-related laboratory abnormalities do not require treatment discontinuation except:

- ◆ Grade 3 drug-related thrombocytopenia > 7 days or associated with bleeding requires discontinuation
- ◆ Grade  $\geq$  3 drug-related AST, ALT or Total Bilirubin requires discontinuation\*
- ◆ Concurrent AST or ALT > 3 x ULN and total bilirubin > 2 x ULN

\*In most cases of Grade 3 AST or ALT elevation, study treatment will be permanently discontinued. If the investigator determines a possible favorable benefit/risk ratio that warrants continuation of study treatment, a discussion between the investigator and the BMS Medical Monitor/designee must occur.

- Any Grade 4 drug-related AE or laboratory abnormality, except for the following events which do not require discontinuation:
  - Grade 4 neutropenia  $\leq$  7 days
  - Grade 4 lymphopenia or leukopenia or asymptomatic amylase or lipase
  - Isolated Grade 4 electrolyte imbalances/abnormalities that are not associated with clinical sequelae and are corrected with supplementation/appropriate management within 72 hours of their onset
  - Grade 4 drug-related endocrinopathy AE, such as adrenal insufficiency, hyper- or hypothyroidism, or glucose intolerance, which resolve or are adequately controlled with physiologic hormone replacement (corticosteroids, thyroid hormones) or glucose-controlling agents, respectively, may not require discontinuation after discussion with and approval from the Medical Monitor.
- Any event that leads to interruption in dosing lasting > 6 weeks from the previous dose requires discontinuation, with the following exceptions:
  - Dosing delays to allow for prolonged steroid tapers to manage drug-related adverse events are allowed.
  - Dosing delays lasting > 6 weeks from the previous dose that occur for non-drug-related reasons may be allowed if approved by the BMS Medical Monitor (or designee).
- Any AE, laboratory abnormality, or intercurrent illness which, in the judgment of the Investigator, presents a substantial clinical risk to the subject with continued nivolumab dosing.

Prior to re-initiating treatment in a subject with a dosing delay lasting > 6 weeks, the BMS Medical Monitor (or designee) must be consulted. Tumor assessments should continue as per protocol even if dosing is delayed. Periodic study visits to assess safety and laboratory studies should also continue every 6 weeks or more frequently if clinically indicated during such dosing delays.

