#### **4.5.4 Management Algorithms for Immuno-Oncology Agents**

Immuno-oncology (I-O) agents are associated with AEs that can differ in severity and duration than AEs caused by other therapeutic classes. Nivolumab is considered an immuno-oncology agent in this protocol. Early recognition and management of AEs associated with immuno-oncology agents may mitigate severe toxicity. Management Algorithms have been developed to assist investigators in assessing and managing the following groups of AEs:

- Gastrointestinal
- Renal
- Pulmonary
- Hepatic
- Endocrinopathy
- Skin
- Neurological

The above algorithms are found in the nivolumab IB and in [Appendix 2](#).

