## Endocrinopathy Management Algorithm

Rule out non-inflammatory causes. If non-inflammatory cause, treat accordingly and continue I-O therapy. Consider visual field testing, endocrinology consultation, and imaging.

[figure not shown]
Patients on IV steroids may be switched to an equivalent dose of oral corticosteroids (e.g. prednisone) at start of tapering or earlier, once sustained clinical improvement is observed. Lower bioavailability of oral corticosteroids should be taken into account when switching to the equivalent dose of oral corticosteroids.

Updated 05-Jul-2016

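### Controlled Grade 4 drug-related adrenal insufficiency must stop treatment under Protocol 4.5.2 but may continue under the Grade 4 exception in 4.5.3

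*Protocol*

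**What the plan says.** Protocol 4.5.2 (Criteria to Resume Treatment) first lets subjects whose drug-related endocrinopathy is controlled by physiologic hormone replacement restart after the Medical Monitor has been consulted. It then takes one condition out of that allowance: "Adrenal insufficiency requires discontinuation regardless of control with hormone replacement". No grade is attached.

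Protocol 4.5.3 (Dose Discontinuation Criteria) treats the condition twice. Under Grade 3, controlled endocrinopathies need not stop, and the adrenal insufficiency sentence follows again in identical words. Under Grade 4, the listed exceptions to discontinuation include a "Grade 4 drug-related endocrinopathy AE, such as adrenal insufficiency, hyper- or hypothyroidism, or glucose intolerance", on the condition that these are events "which resolve or are adequately controlled with physiologic hormone replacement (corticosteroids, thyroid hormones) or glucose-controlling agents, respectively". Such events "may not require discontinuation after discussion with and approval from the Medical Monitor".

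Protocol 3.5 lists the reasons for which a subject must stop and includes the criteria of 4.5.3; it does not name 4.5.2. The last criterion in 4.5.3 also requires stopping for any event that the investigator judges to carry substantial clinical risk if dosing continues.

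On the management algorithms, 4.5.4 says "The above algorithms are found in the nivolumab IB and in" Appendix 2, and Appendix 2 opens with "These general guidelines constitute guidance to the Investigator and may be supplemented by discussions with the Medical Monitor representing the Sponsor".

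**The concern.** A mandatory stopping rule should give one answer for one event. Here an investigator with a subject whose Grade 4 drug-related adrenal insufficiency is well controlled on replacement can cite the protocol either way. Stopping complies with both sections. Continuing under an approved waiver complies with the Grade 4 exception but breaches 4.5.2. Similar subjects could be handled differently at different sites, and a waiver properly obtained under 4.5.3 could be recorded as a deviation from 4.5.2.

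The rule still matters after enrollment stopped, because subjects may be treated for up to 2 years from the first randomized dose (Protocol 3.1 and 4.5).

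**Working it through.** No arithmetic applies. The check sets the current rules side by side for drug-related adrenal insufficiency controlled with physiologic hormone replacement.

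| Place in the protocol | Grade covered | Result |
|---|---|---|
| 4.5.2, adrenal insufficiency sentence | none stated | stop |
| 4.5.3, Grade 3 endocrinopathy bullet | 3 | stop |
| 4.5.3, Grade 4 exception | 4 | may continue with Medical Monitor approval |

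1. *Does limiting the sentence in 4.5.3 to Grade 3 reconcile the text?* That sentence sits in a Grade 3 sub-bullet, so the limit is a fair reading. It leaves Grade 3 having to stop while the more severe Grade 4 may continue, and the ungraded sentence in 4.5.2 still conflicts with the exception.

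2. *Does the more specific rule win?* The Grade 4 exception is specific by grade; the sentence in 4.5.2 is specific by event. Neither section says which prevails.

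3. *Does Section 3.5 settle it?* It points to 4.5.3 as the mandatory list. But the sentence in 4.5.2 is worded as a requirement to discontinue, and a subject whose dosing has been held must meet 4.5.2 to restart. The reversed ordering of Grades 3 and 4 lies inside 4.5.3, where 3.5 cannot help.

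4. *Does Medical Monitor involvement settle it?* Section 4.5.2 already offers a Medical Monitor route for controlled endocrinopathies and then excludes adrenal insufficiency from it. The Grade 4 exception reopens the kind of route that 4.5.2 closes.

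5. *Does the algorithm settle it?* Appendix 2 presents its algorithms as guidance. The endocrinopathy page carries general text such as "Consider visual field testing, endocrinology consultation, and imaging", but its figure is not reproduced in the copy reviewed, so nothing is inferred from it in either direction.

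6. *How common is the event?* The protocol gives rates only for the whole endocrine category, Grades 3-4 combined, in two earlier trials: 0 of 131 nivolumab subjects in CA209017 (Table 1.4.2-1) and no more than 3% in CA209057 (Section 1.4.2). Neither isolates adrenal insufficiency or Grade 4, so no expected count can be given for this trial.

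**The case against.** The best defense is that 4.5.3 governs discontinuation, because Section 3.5 names it and not 4.5.2, and that within 4.5.3 the Grade 4 exception is the rule written for Grade 4. The exception is permissive, requires both discussion and approval, and sits beside the investigator-judgment stop, so a waiver is a reviewed decision and not a site's free choice. Subjects have also already tolerated pre-study nivolumab, which makes a new severe event less likely.

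Much of this stands as a limit on the risk. It does not explain why Grade 3 should be stricter than Grade 4, and it does not remove the sentence in 4.5.2.

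Three stronger readings are tempting and not supported:

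- *That resolved events conflict just as plainly.* The strict sentence speaks of control with hormone replacement, not of resolution. The conflict is clear for controlled events and less explicit for resolved ones.
- *That the protocol leaves subjects unprotected.* The approval step and the investigator-judgment stop both remain in force.
- *That the trial's comparison is biased.* The rules are the same in both arms, and stopping study drug is not in itself an event or a censoring reason in the SAP's PFS scheme (Table 4.1-1).

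It is also fair to say that the current text does not prove which rule was intended. The change history in Appendix 4 records the strict sentence as a safety update to both sections under Revised Protocol 04 and lists no matching edit to the Grade 4 exception. That is consistent with an exception left unaligned, but it is context only; the point rests on the current text.

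**Conclusion.** The inconsistency is real in the current protocol. For drug-related Grade 4 adrenal insufficiency adequately controlled with physiologic replacement, 4.5.2 requires stopping and 4.5.3 permits continuing with approval. Inside 4.5.3 the more severe grade gets the more lenient rule. Section 3.5 resolves neither.

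This is a minor internal inconsistency in a safety rule. The event is likely rare, though its frequency cannot be estimated from the documents; a cautious site can comply with both sections by stopping; and no efficacy analysis is affected. The conclusion rests on reading the sentence in 4.5.2 as it stands, without a grade limit, and on the visible text of Appendix 2 only.

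**What to change.** In the Grade 4 exception of 4.5.3, delete *adrenal insufficiency*. Delete *respectively* too, since the examples and treatments would no longer pair off. Keep *corticosteroids*: the list of examples is open-ended, and SAP 7.6.6 names hypophysitis separately from adrenal insufficiency, so other endocrinopathies managed with physiologic corticosteroid replacement should keep the route.

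Because the list is open-ended, deletion alone is not enough. In both 4.5.2 and 4.5.3, amend the existing adrenal insufficiency sentence so that it begins with *drug-related* and ends by saying that Grade 3 and Grade 4 events are included. In 4.5.3, place it where it clearly governs both grades and not inside the Grade 3 bullet alone. The drug-related limit matters: exclusion criterion 2c and Sections 3.4.2 and 3.4.3 allow subjects on adrenal replacement steroids, and an unqualified rule could be read as reaching them. The same revision could say whether a resolved event is covered.

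If the sponsor in fact wants the waiver, the sentence in 4.5.2 and the Grade 3 bullet would have to change instead. Either way, one rule should remain.

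The cost is a short wording change. It needs IRB/IEC approval under Section 9.1.1 and can go into the next protocol revision. The recommended direction also means that a rare subject with controlled Grade 4 adrenal insufficiency loses the case-by-case waiver.
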